11.2 Listings

Subject Accountability

1. Randomization List (including, subject ID, randomization number, randomized treatment and treatment administered, and date of treatment)
2. Inclusion and Exclusion Criteria
3. Protocol Deviations
4. Subjects Withdrawing from the Study Prematurely (date and reason)
5. Analysis Populations with Reason for Exclusion (if populations differ)

Demographics and Baseline Characteristics

6. Demographics and Baseline Characteristics [age, sex, race, ethnicity, weight, height, BMI]
7. Medical History
8. Baseline Medication Use

Efficacy

9. Mortality Data, if applicable
10. SP02 Data
11. ARDS Data and Intubation Data
12. ICU and Hospital LOS Data
13. Ordinal Scale Data

Safety

14. All Adverse Events [with indication of TEAE]
15. Hematology Data [with flagging of values outside of normal range]

16. Chemistry Data [with flagging of values outside of normal range]
17. Vital Signs Data [with flagging of values outside of normal range]
18. ECG data

11.3 Figures

Note that all figures, unless otherwise stated, will be line plots showing mean \pm SEM at each visit for each treatment arm.

19. Summary of All-cause mortality over time [Time to event Graph]

12. HANDLING OF MISSING OR INCOMPLETE DATES FOR ADVERSE EVENTS AND CONCOMITANT MEDICATIONS

12.1 Imputation Rules for Partial or Missing Stop Dates

If the month and year are present, impute the last day of the month. If only the year is present, impute December 31 of that year. If the stop date is entirely missing, assume the event or medication is ongoing. If a partial or complete stop date is present and the 'ongoing' or 'continuing' box is checked, then it will be assumed that the AE or concomitant medication stopped and the stop date will be imputed, if partial.

		Stop Date						
		Complete: yyyymmdd		Partial: yyyymm		Partial: yyyy		Missing
Start Date		<1 st Dose	≥1 st Dose	<1 st Dose yyyymm	≥1 st Dose yyyymm	<1 st Dose yyyy	≥1 st Dose yyyy	
Partial: yyyymm	=1 st Dose yyyymm	1		1		N/A	1	1
	≠ 1 st Dose yyyymm		2		2			
Partial: yyyy	=1 st Dose yyyy	3	1	3	1	N/A	1	1
	≠ 1 st Dose yyyy		3		3			
Missing		4	1	4	1	4	1	1

1 = Impute the date of first dose 2 = Impute the first of the month 3 = Impute January 1 of the year

4 = Impute January 1 of the stop year

Note: For subjects who were never treated (first dose date is missing), partial start dates will be set to the first day of the partial month.

Note: If the start date imputation leads to a start date that is after the stop date, then do not impute the start date.

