### Concomitant Medications

Concomitant medications will be collected from the medical records: prior (pre-hospitalization) concomitant medications, in-patient concomitant medications.

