8.1 Handling of Missing and Incomplete Data

All data collected under this study protocol will be included in the assessment of patient safety. Missing or incomplete AE data will assume greatest relationship to study drug and/or severity.

Incomplete adverse event and concomitant medication dates will be imputed as described in Section 11. If imputed dates are used, then they will be identified as such in the final study report. If an AE start date is missing or partially missing and no additional information is available in order to establish whether the event started before or after the dose of study drug, the event will be considered to have started after dose. Partially missing dates where the month and year is prior to Day 0 will not be classified as post dose.

For the ordinal score effectiveness endpoint analysis of clinical outcomes at Day 5 and Day 28 a sensitivity analysis will be performed for all patients that have been discharged from the hospital, cannot be reached via telephone contact, and their death status is not known. The sensitivity analysis will be performed where missing ordinal scale status at Day 5 and Day 28 will be replaced as having died (Ordinal score 8).

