9.5.2 Concomitant Medications

The number and percent of patients receiving concomitant medications or treatments prior to and during the study and at the final visit will be tabulated and presented overall and by treatment group for the ITT analysis dataset. Concomitant medications and treatments will be summarized using descriptive statistics and will be presented by type of drug (WHO DRUG classification preferred term and Anatomical Therapeutic Chemical Classification [ATC] level 1) overall and by treatment group for the safety and ITT analysis populations. There should be no significant differences in the use of concomitant treatments between groups. All concomitant therapies will be recorded to be able to compare any inadvertent imbalances between the groups.

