11.1.3 Safety (Analysis population: Safety)

11.1.3.1	Overall Summary of Treatment-Emergent Adverse (TEAE) Events
11.1.3.2	Incidence of TEAEs by System Organ Class and Preferred Term
11.1.3.3	Incidence of Treatment-Emergent Related AEs by System Organ Class and Preferred Term
11.1.3.4	Incidence of Treatment-Emergent Serious Adverse Events (SAEs) by System Organ Class and Preferred Term
11.1.3.5	Incidence of TEAEs by Preferred Term in Descending Order of Frequency
11.1.3.6	Incidence of Treatment-Emergent Related AEs by Preferred Term in Descending Order of Frequency

11.1.3.7.1	Summary of Hematology
11.1.3.7.2	Summary of BioChemistry
11.1.3.8.1	Summary of Vital Signs and Change from Baseline over Time (bpm)
11.1.3.8.2	Summary of ECG Results
11.1.3.8.3	Summary of Medical History
11.1.3.9.1	Concomitant Medication Use by ATC Level 1
11.1.3.9.2	Concomitant Medications Descending Order of Use
11.1.3.9.3	Medication Started on Study in Descending Order of Use
11.1.3.9.4	Concomitant ARDS therapies Started on Study in Descending Order of Use

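### SAP Section 12 dates a continuing medication with an unknown start to the day of first dose, even when it is recorded as a pre-hospitalization or baseline drug

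*SAP*

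**What the plan says.** SAP Section 12 is titled "HANDLING OF MISSING OR INCOMPLETE DATES FOR ADVERSE EVENTS AND CONCOMITANT MEDICATIONS", and SAP 8.1 confirms that medication dates fall under it: "Incomplete adverse event and concomitant medication dates will be imputed as described in Section 11". (The rules are in Section 12, so that cross-reference is off by one. The only subsection heading, 12.1, mentions stop dates, although its grid imputes start dates.)

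The grid crosses what is known of the start with what is known of the stop. Two codes matter here: "1 = Impute the date of first dose" and "4 = Impute January 1 of the stop year". For stop dates, a month-only date becomes the last day of the month. For a year-only date the rule is "If only the year is present, impute December 31 of that year". A wholly missing stop is treated as ongoing.

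The outputs that depend on medication timing are Table 11.1.3.9.3, "Medication Started on Study in Descending Order of Use", its companion 11.1.3.9.4 for ARDS therapies, and the SAP 9.5.2 counts of medications, which "prior to and during the study and at the final visit will be tabulated". The SAP does not define started on study.

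Protocol 5.2 collects medications in two categories: "prior (pre-hospitalization) concomitant medications, in-patient concomitant medications". Protocol 5.1.2 also has concomitant medications recorded at the Day 1 visit before treatment.

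**The concern.** For an adverse event, moving an unknown onset to first dose is a deliberately cautious choice, because the event becomes treatment-emergent. SAP 8.1 gives that default in words for adverse events only, and makes it conditional on there being no other information about whether the event began before or after dosing.

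The reasoning does not carry over to medications. A home drug of uncertain start that continues through the admission was not started on study, and moving it to the first-dose date is an error rather than a cautious choice. Other information does exist, because the trial records whether a drug is pre-hospitalization and what was in use before the first dose. Section 12 uses neither.

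At stake is how well the medication tables describe the trial. SAP 9.5.2 says that therapies are recorded so that inadvertent imbalances between arms can be seen. A table of drugs started after randomisation that also holds drugs patients were already taking serves that purpose less well.

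**Working it through.** No planned figure is involved, so the check is a reading of the grid. The extracted table has blank cells in some partial-date rows, possibly merged cells, so I rely only on the two rows that are fully legible.

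**Stop-date columns, in order:** complete before / on or after first dose; month-only before / on or after; year-only before / on or after; missing.

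| Start date | Codes across the seven columns |
|---|---|
| Wholly missing | 4, 1, 4, 1, 4, 1, 1 |
| Year only, equal to the dosing year | 3, 1, 3, 1, N/A, 1, 1 |

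**Result for a missing start.** Four of the seven columns give the first-dose date: the three with a stop on or after first dose, and the one with no stop. The other three, all with a stop before first dose, give January 1 of the stop year, and those drugs stay prior. The dosing-year row behaves the same way: code 1 in the same four columns, and January 1 of the year (code 3) or not applicable in the others.

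**Case A: home drug, both dates unknown.** A missing stop means ongoing, so the last column applies and code 1 sets the start to first dose. If started on study means a start on or after first dose, the drug is counted there and no longer as prior.

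**Case B: course finished before first dose, start unknown, stop recorded only as the dosing month.** The partial stop is not earlier than the dosing month, so the on-or-after column applies and code 1 sets the start to first dose. The stop becomes month end. Section 12's safeguard withholds an imputed start that falls after the stop. It does not trigger, because month end is on or after first dose. A finished course becomes one that begins at first dose.

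**Case C: year-only stop in the dosing year.** The stop becomes 31 December, with no cap at death, last contact or end of study (Day 60 in SAP 5.7). The drug can therefore appear to be in use at the final visit.

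**Case D: stop date known to be before first dose, start unknown.** Code 4. Not affected.

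**Illustration of size, on assumed inputs only.** Let p be the true proportion starting a drug class on study, and f the proportion of the remaining patients given a false on-study start, equal in both arms. The observed proportion is p + (1 − p)f, so a between-arm difference shrinks to (1 − f) of its true value. For assumed true proportions of 15% and 30% (15 points):

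| f | First arm | Second arm | Difference |
|---|---|---|---|
| 10% | 0.15 + 0.85×0.10 = 23.5% | 0.30 + 0.70×0.10 = 37.0% | 13.5 points |
| 20% | 0.15 + 0.85×0.20 = 32.0% | 0.30 + 0.70×0.20 = 44.0% | 12.0 points |
| 40% | 0.15 + 0.85×0.40 = 49.0% | 0.30 + 0.70×0.40 = 58.0% | 9.0 points |

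None of these proportions or values of f comes from the documents. The dilution also requires that the false starts fall in the same drug class as the real difference.

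**The case against.** The strongest reply is that the misclassification is inferred. The SAP neither defines started on study nor says that the tables are built from imputed dates, so a programmer could use the pre-hospitalization category, the baseline record or Listing 8 (baseline medication use) instead. That stands as far as it goes: the count follows from the natural reading, not from an explicit statement. The date itself is not inferred. Section 12 assigns it, and nothing says that the recorded category takes precedence.

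The reply also limits the reach of the point, and these limits stand:

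- A reader might infer that every home or pre-randomisation drug with an unknown start is counted as started on study. The grid does not support that: a stop known to precede first dose gives code 4.
- A reader might infer that these tables are the trial's only view of background care. They are not: Listing 8 and Tables 11.1.3.9.1 and 11.1.3.9.2 also show medication use. In SAP 9.5.2, an ongoing home drug is rightly counted as used during the study whichever start date it carries.
- A reader might infer that the ARDS-therapy table is seriously distorted. Protocol 7.3 asks for start and stop dates for every medication, and Protocol 5.2 draws them from medical records. Treatments given in hospital should usually have charted dates, so Table 11.1.3.9.4 is little exposed.
- The rule is the same in both arms of a blinded trial, and no efficacy or safety test uses medication start dates.

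**Conclusion.** The point holds in a limited form. For medications with a wholly missing start, or a start known only to the dosing year, that are ongoing, have no stop date, or have a stop recorded or classified as on or after first dose, Section 12 assigns the first-dose date. It makes no exception for drugs the trial has itself recorded as pre-hospitalization or in use at baseline. This is a stated rule that gives a wrong date, not merely missing detail.

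The likely result is some inflation of Table 11.1.3.9.3 and a matching loss from the prior count in SAP 9.5.2. Both rest on reading started on study as a start on or after first dose. The effect is confined to descriptive tables, and no primary or secondary test changes. Its size is unknown, and the dilution figures above show direction and form only. They do not support a claim that a treatment comparison in this trial would be materially biased.

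**What to change.** In SAP Section 12, keep the first-dose default for adverse events and add a separate rule for medications:

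1. Define started on study as a start after first dose, and state that a first-dose date assigned under item 3 counts as one.
2. Class any drug recorded as pre-hospitalization, or listed at the pre-dose baseline visit, as prior (and as concomitant if ongoing), whatever its imputed date.
3. Apply the first-dose default only to drugs recorded as in-patient and not in use at baseline. Classing every missing start as prior would go too far, because it would hide in-patient drugs begun after randomisation.
4. Cap imputed medication stop dates at the earliest of death, last contact or end of study. Leave adverse-event stop dates to Protocol 8.3, which follows events continuing at study exit for 30 days, to resolution, or until no improvement is expected. A Day 60 cap would conflict with that.

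In the same edit, correct the cross-reference in SAP 8.1 and give the start-date grid its own heading.

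The cost is SAP wording and a few lines of programming, with no new data. One small weakness remains: an in-patient drug given before first dose but not captured at baseline could still be counted as started on study.

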11. VERSION HISTORY

Number	Effective Date	Version (Principal changes from previous version)
Version 1.0	21 April 2022	Initial version
